### **Study protocol**

**Randomization:** At baseline we will randomly assign participants through computer-generated allocation sequence. We anticipate minimal risk of contamination but will survey participants about whether they have discussed the intervention with other participants. We considered alternative designs, including a waitlist control condition or an active treatment arm without the *novela* but these were deemed impractical for the pilot intervention.

**Baseline and exit assessment and interview visits:** At baseline assessment, study staff will evaluate participants using instruments to measure demographics and self-perceived barriers to care for Hispanic immigrant populations. Study interviews to administer the questionnaires will last up to 4 hours and will occur in a private room at the clinic or community-based organization. Participants will receive \$40 in gift card and \$10 transportation for completing this study visit. Study staff will offer a meal or meal ticket and allow for breaks as needed by the participant. The instruments we have selected are based on published evidence of barriers to HIV care in Latino immigrants, our qualitative research, and framed by our adapted Andersen Model of Health Care Utilization. Consistent with this conceptual model, instruments will measure the environment (e.g. neighborhood characteristics and access to services); predisposing individual-level factors (e.g. acculturation, family cohesion, social position, depression, substance use); individual enabling factors (e.g. self-efficacy, patient activation, cultural norms); and perceived health care need. We have selected scales that as much as possible have been validated in a Spanish-speaking low-literacy population. Most of the measures have been developed and validated by a national epidemiological survey in Latinos led by members of the study team that have strong reliability and validity in Spanish-speaking populations. For scales that have no prior Spanish language translation, the study team composed of multi-national native-Spanish speaking investigators, have performed translations and reviewed the translations for accuracy of content. Study staff will guide the participant through questions administered on REDCAP. If REDCAP is not available at the time of administration, questions will be documented on paper and subsequently uploaded to REDCAP. Latino immigrants have numerous barriers that may inhibit their ability to participate in research (e.g. multiple jobs, lack of access to transportation, family responsibilities). In the event, that the participant cannot come in person for the study visit and requests to participate in the baseline or exit assessment and interview visits by telephone, study staff will arrange to conduct the interview by telephone in a private room with the conversation recorded for accuracy and fidelity. Answers to the questionnaires will be documented in REDCAP by study staff. While we will attempt to obtain all exit assessments and interviews (quantitative measurements and qualitative feedback) at week-24, we will allow a window of approximately 2 weeks prior and 4 weeks after the week-24 date to accommodate participants' availability.

**CHW-delivered questionnaires:** At each CHW session, the CHW will also administer a 3 item questionnaire covering antiretroviral adherence, perceived need for HIV care, and global effort needed to attend HIV visits.

**Intervention evaluation:** To ensure fidelity of the intervention, we will obtain client consent to audio record the sessions. The CHW will also provide a brief written survey for the participant to complete on feedback for the session. Responses will be anonymous. Study staff will also conduct an exit assessment and interview with participants. During the interview study staff will use qualitative methods to assess impressions and ideas for improvement on the intervention process including suitability of the instruments to assess risk factors for inconsistent HIV clinic

**Official title:** Retention in HIV Care for Hispanic Immigrants (ADELANTE)

**NCT number:** NCT03484117

**Document date:** 4/7/2022

attendance. The CHW will likewise complete an exit survey to solicit feedback for improvement. Study staff will present de-identified results to a Latino/HIV oriented community advisory board, to discern the need for iterative revisions of the intervention manual and intervention design. Study staff will make revisions to the questionnaire content to account for participant feedback on acceptability of the content and feasibility based on duration to complete the questionnaire. We estimate a need to enroll 100 individuals to randomize 75. Estimated conservative rate of attrition is 30%. This sample size is consistent with recommendations for randomized pilot studies for preliminary estimation of effect sizes and lower bounds. The primary purpose of our pilot is to determine the feasibility of the intervention program and evaluation protocols, including treatment acceptability, data collection procedures, and expected eligibility, recruitment time and effort, and follow-up rates. Given the small sample size, we will not be able to determine intervention efficacy; rather, our analyses will be mainly descriptive and will focus on confidence interval estimation. The primary focus is to assess feasibility and acceptability of the CHW+*telenovela* intervention and its impact on retention in care. Study staff will measure attended HIV primary care visits over weeks 0-16 and 17-32 weeks as well as CD4 and HIV RNA from the electronic medical record at week-24 and week-48, to assess short and long-term effects of the intervention. To obtain further information on feasibility and acceptability of the instruments at baseline and exit assessment and interview visits, study staff will present portions of the questionnaires to a focus group of Latino HIV peer workers with extensive experience working with the population, drawn from local HIV-related community advisory boards or AIDS service organizations. Study staff will present instruments to the group and perform cognitive debriefing to ascertain if the items are conveying the intended meaning. We will also receive additional feedback on acceptability of format and content. We will also ask work with these community colleagues to perform back translation from Spanish to English on items created by the study team to confirm preservation of content. We will reimburse these individuals each for \$40 for two hours of service.

**Data analysis:** We will compare baseline distributions of key demographic and outcome variables for comparability between intervention and control groups using nonparametric tests. The pre-specified primary outcome was retention in care. We defined this outcome as having at least one visit attended in HIV clinic at both time periods (weeks 1-16 and 17-32) post-randomization. These definitions are consistent with consensus guidelines on visit consistency. Two study staff blinded to randomization allocation, extracted HIV primary care appointment history from the medical record with disagreements reconciled by a third reviewer. An HIV primary care appointment was defined as an appointment with an HIV provider, meaning a health care provider (e.g., physician or mid-level provider) who could prescribe antiretroviral treatment. The prespecified secondary outcomes were proportion with viral suppression (HIV RNA<200 copies/ml) and change in CD4 count (cells/microliter) from baseline to weeks-24 and -48 post-randomization, extracted from the medical record. Obtaining a measure of effect size may not be justified given the limited sample size but we will use these data to inform power calculations for a subsequent large-scale trial with attention to matched-arms in an R01. Participant sociodemographic and clinical characteristics were summarized by intervention allocation with Chi-square tests and t-tests. The primary outcome of RIC and secondary outcomes of viral suppression and CD4 count at weeks-24 and -48 were compared by group using Chi-square tests. Statistical significance was defined by two-sided  $p \leq 0.05$ . Analyses were conducted using SAS version 9.4 (SAS Institute, Cary, NC).

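### Do the planning figures of 100 enrolled, 75 randomised and 30% attrition contradict each other?

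*Combined protocol and SAP*

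**What the plan says.** All the sample-size reasoning sits in a few sentences under Intervention evaluation. The first two give the counts and then the loss rate: "We estimate a need to enroll 100 individuals to randomize 75. Estimated conservative rate of attrition is 30" per cent. The third gives the basis: "This sample size is consistent with recommendations for randomized pilot studies for preliminary estimation of effect sizes and lower bounds". The text does not say at which stage the 30% applies, why 100 become 75, or how many participants are expected to complete the exit assessment.

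Four other statements bear on the point:

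- Randomization section: "At baseline we will randomly assign participants through computer-generated allocation sequence". No allocation ratio is given.
- Intervention evaluation: efficacy is ruled out as an aim at this size, and "our analyses will be mainly descriptive and will focus on confidence interval estimation".
- Baseline and exit assessment and interview visits: the exit assessment is due at about week 24 and requires contact with the participant, in person or by telephone.
- Data analysis: the primary outcome (retention in care) and the secondary outcomes (viral suppression and CD4 count) are taken from the medical record. A two-sided significance level is stated there, but it plays no part in setting the sample size.

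**The concern.** Three numbers stand side by side and invite the reader to link them, and the obvious link fails: 75 out of 100 is a 25% loss, not 30%. If the 30% is meant to explain the step from enrolment to randomisation, one of the three figures is wrong. If it is meant as loss after randomisation, the step from 100 to 75 has no stated reason, and the number who will supply exit data is well below 75.

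The plan justifies its size by the estimates the pilot will give, with confidence intervals as the main product. If those estimates rested on about 52 people rather than 75, the intervals would be wider than a reader of the sample-size text would expect. Follow-up rates are also among the things the pilot sets out to learn, so an expected rate with no stage or denominator is a poor yardstick for the observed one.

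**Working it through.** **Inputs from the plan.** Enrolled 100; randomised 75; attrition 30% (Intervention evaluation). Source of the named outcomes: medical record (Data analysis).

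**Assumed, not in the plan.** 1:1 allocation; illustrative true proportions of 85% against 70%, and of 50% in both arms.

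**Step 1: can the plan's figures be reproduced?**

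- Loss implied by the two counts: 1 − 75/100 = 25%.
- 30% lost before randomisation, starting from 100: 100 × 0.70 = 70, against 75 stated.
- 30% lost before randomisation, aiming for 75: 75/0.70 = 107.1, so 108, against 100 stated.
- Multiplying up instead of dividing: 75 × 1.30 = 97.5, so 98. This comes near 100 but is not the correct inflation for dropout, and nothing shows that it was used.

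So 30% does not produce the step from 100 to 75. A 25% loss does (75/0.75 = 100), but the plan does not state that rate.

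**Step 2: 30% lost after randomisation.** 75 × 0.70 = 52.5, so about 52 with exit data, or 26 per arm under 1:1 allocation. On this reading 100 → 75 is one loss and 75 → 52 is a later one. Both can be true together.

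**Step 3: effect on precision.** The half-width of a 95% Wald interval for a difference in proportions is 1.96 × √(p₁q₁/n₁ + p₂q₂/n₂), where q = 1 − p.

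| Arm sizes | 85% vs 70% | 50% vs 50% |
|---|---|---|
| 38 / 37 (75 in total) | 18.6 points | 22.6 points |
| 35 / 35 (70 in total) | 19.2 points | 23.4 points |
| 26 / 26 (52 in total) | 22.3 points | 27.2 points |

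From 75 to 70 the half-width grows by 0.6 or 0.8 points. From 75 to 52 it grows by 3.7 or 4.6 points; 22.3/18.6 and 27.2/22.6 are both about 1.20.

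**Step 4: which outcomes would the smaller number affect?**

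- Retention in care is defined by attended visits found in the clinic record in each of two periods. A participant with no visit in a period counts as not retained; that is an outcome value, not a missing one.
- Viral load and CD4 count also come from the record. They may be missing for people who stop attending, but the plan does not tie the 30% to that.
- Exit questionnaires and interviews do depend on follow-up, so the 52 applies to them. The plan names no between-arm binary endpoint from the exit questionnaires, so the last row of the table illustrates scale and does not describe a planned analysis.

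**The case for a change.** The strongest case for a change is that the 30% directly follows the two counts, so many readers will take it as their explanation, and on that reading the figures conflict. On the other reading, the plan omits the expected number of exit assessments, although acceptability feedback depends on them and follow-up is something the pilot wants to measure. Two or three sentences would settle the matter without adding participants.

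Much of this is fair as a comment on drafting. The stage of the 30% is unstated, and the expected number with exit data has to be worked out by the reader. Three parts of the case do not stand:

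- The conflict exists only if the 30% explains the step from 100 to 75, and the text does not say that it does.
- The plan does not promise 75 participants with complete data; it says that 75 will be randomised.
- The plan says that the data collected will inform the later trial's power calculations, and it lists follow-up rates among the things to be determined. The observed rate, with its own denominator, therefore replaces the 30%. The plan sets no progression threshold against which the 30% would be judged.

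**Conclusion.** No change to the plan is needed. The arithmetic behind the concern is correct, but it shows missing detail and not an error that would alter a result. On the usual meaning of attrition the figures are compatible: 100 enrolled, 75 randomised and about 52 with exit data. On the other reading the discrepancy is 5 participants (70 against 75), worth less than one percentage point of half-width.

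On either reading no stated target is missed, because the size rests on general pilot-study recommendations and not on power or precision, and the analyses are declared mainly descriptive. The analysts will report the numbers enrolled, randomised and followed up as they occur, and each interval will reflect the number that actually contributed to it. Writing the stage down would help the reader but would not change the conduct, the analysis or the conclusions.

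This judgement rests on the medical record being available for essentially all those randomised, which the plan implies but does not guarantee. The precision figures also rest on 1:1 allocation and on the illustrative proportions, none of which the plan states.

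### Do the two labels for the first retention window, weeks 0-16 and weeks 1-16, leave the primary outcome undefined?

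*Combined protocol and SAP*

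**What the plan says.** The Intervention evaluation section, in its text on outcome measurement, states that staff will measure "attended HIV primary care visits over weeks 0-16 and 17-32 weeks". The Data analysis section states "The pre-specified primary outcome was retention in care" and defines it as "having at least one visit attended in HIV clinic at both time periods (weeks 1-16 and 17-32) post-randomization". The second window is the same in both places; only the start of the first differs.

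Three other statements bear on the point.

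- The Data analysis section says which visits qualify: "An HIV primary care appointment was defined as an appointment with an HIV provider", that is, someone able to prescribe antiretroviral treatment. Two staff blinded to allocation extracted the appointment history, and a third reviewer reconciled disagreements.
- The Randomization section sets the time origin: "At baseline we will randomly assign participants through computer-generated allocation sequence".
- The section on baseline and exit visits places the baseline interview at the clinic or a community organisation, and lets a participant who "requests to participate in the baseline or exit assessment and interview visits by telephone" do so.

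No section defines week 0, week 1 or day 0.

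**The concern.** The primary outcome is binary and needs one attended visit in each window, so a single visit at the edge of the first window can decide a participant's status. Randomisation takes place at baseline and the baseline interview may be held at the clinic, so an HIV-provider visit on the same day is plausible. If the label 0-16 is followed literally, that visit could meet half of the outcome although the intervention could not have influenced it. Counting such visits raises retention in both arms. It would usually dilute an effect that acts on early attendance.

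The stake beyond this pilot is planning. The Data analysis section says "we will use these data to inform power calculations for a subsequent large-scale trial", and both the level of retention and the difference between arms enter such a calculation.

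**Working it through.** **Which visits are in dispute.** The baseline interview is not a qualifying visit, because study staff conduct it and it may be done off-site or by telephone. Only a separate provider visit at the very start matters. A participant changes status only if that is the sole visit in the first window and the participant also attends in weeks 17-32.

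**What the labels can mean.**

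| Reading | First window | Treatment of early visits |
|---|---|---|
| 0-16 as elapsed weeks | day 0 to day 16 × 7 = 112 | day 0 at the boundary |
| 1-16, week 1 = days 1-7 | days 1-112 | day 0 excluded |
| 0-16, week 0 = days 0-6 | days 0-118 (17 × 7 − 1) | day 0 included |
| 1-16, week 0 = days 0-6 | days 7-118 | days 0-6 excluded |

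The first two readings cover the same 112 days apart from day 0. Counted as week labels, 1-16 and 17-32 each span 16 weeks, whereas 0-16 spans 17. The Data analysis wording therefore gives two equal windows and says that they follow randomisation. The measurement text reads naturally as a looser description of the same period.

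**Size, by illustration.** Let q be the share with a provider visit in week 0 (the same in both arms), and let p1 and p2 be the attendance probabilities in the rest of the first window and in the second window, taken as independent. If week-0 visits count,

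retention = [1 − (1 − p1)(1 − q)] × p2.

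None of these inputs is in the documents; all are assumed. Comparison-arm attendance is 78% and 76%; intervention attendance rises to 88% in window 1, 85% in window 2, or both.

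| Effect acts in | Difference, q = 0 | q = 10% | q = 25% | Largest shift |
|---|---|---|---|---|
| Both windows | 15.5 points | 14.9 | 13.9 | −1.6 |
| Window 1 only | 7.6 | 6.8 | 5.7 | −1.9 |
| Window 2 only | 7.0 | 7.2 | 7.5 | +0.5 |

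Worked example, window 1 only, q = 25%: (1 − 0.12 × 0.75) × 0.76 = 0.6916 and (1 − 0.22 × 0.75) × 0.76 = 0.6346, a difference of 0.0570.

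With 75 randomised and an assumed 38/37 split, the expected number reclassified is the sum over arms of n × q × (1 − p1) × p2. This gives 1.0 to 1.3 participants at q = 10% and 2.4 to 3.3 at q = 25%.

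**Comparison with the pilot's precision.** The half-width of the 95% interval for a difference, with n = 37 per arm, is 1.96 × √(2p(1 − p)/n). It is 0.223 at p = 0.6, 0.209 at p = 0.7 and 0.182 at p = 0.8. The largest shift above, 1.9 points, is about a tenth of that.

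**Direction of error in the illustration.** Here q covers the whole of week 0. If the first window is days 1-112, visits on days 1-6 still count, and only the day-0 part of q is in question. On that reading the table overstates the effect.

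**The case for a change.** The strongest case for a change is that both statements are current text, they concern the primary outcome, and they do not match. Blinded extraction and a third reviewer cannot supply a rule that is not written: two careful extractors could treat a same-day visit differently. The elapsed-weeks reading is also not perfectly tidy, since 17-32 read as elapsed weeks would leave the days between week 16 and week 17 in neither window. And one participant is worth about 2.7 points in an arm of 37 (1/37).

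The mismatch of labels and the lack of a day rule stand. The consequences do not follow to the same degree. The words placing the windows after randomisation exclude earlier visits, so only same-day visits, or at most those in the first week, are open. The appointments are dated, so one convention can be applied uniformly.

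A larger effect on the level of retention is conceivable. If 10% of participants had the critical pattern, about 4 per arm would change status (37 × 0.10 = 3.7). Under the attendance rates above, however, (1 − p1) × p2 is at most 0.22 × 0.85 = 0.187. Reaching 10% would then require more than half of participants to have a week-0 provider visit (0.10/0.187 = 53%). Nothing in the documents points to that, or rules it out.

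**Conclusion.** This is a loose label together with a small missing detail, and an analyst who follows the Data analysis section obtains a sound primary outcome. That section alone defines retention, limits both windows to time after randomisation and gives them equal length. The choice left open, how to treat a visit on day 0, is ordinary analytic detail. It is made without reference to arm and is reported with the result.

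Under the assumed inputs the difference in retention moves by 0.2 to 0.8 points at q = 10% and by 0.5 to 1.9 points at q = 25%, and its direction depends on where the effect acts. The effect is nil if no one has a week-0 provider visit. Against a half-width of about 18 to 22 points, in a pilot whose analyses are meant to be mainly descriptive, this alters no conclusion. For planning the next trial, sampling error in the pilot's estimates far exceeds the ambiguity, and the plan itself doubts that an effect size from so small a sample is justified.

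The judgement rests on three assumptions: week-0 provider visits are about equally common in the two arms, as randomisation leads one to expect; one convention is used for everyone; and the critical pattern (a same-day visit, no other in 16 weeks, then attendance in weeks 17-32) is uncommon.

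### The Chi-square test named for CD4 does not fit an outcome defined as a change in count; a lesser point is that the denominator for viral suppression is unstated although whether a result exists can depend on arm

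*Combined protocol and SAP*

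**What the plan says.** All the relevant text is in the Study protocol section of the combined document.

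- **Outcomes.** The Data analysis paragraph defines two secondary outcomes: the proportion with HIV RNA below 200 copies/ml, and the change in CD4 count in cells/microliter. They run "from baseline to weeks-24 and -48 post-randomization, extracted from the medical record". The Intervention evaluation text likewise takes "CD4 and HIV RNA from the electronic medical record at week-24 and week-48". No study blood draw is described.
- **Test.** The "secondary outcomes of viral suppression and CD4 count at weeks-24 and -48 were compared by group using Chi-square tests", with significance at two-sided 0.05. No CD4 categories or cut-points are given, and this sentence refers to CD4 count at the two weeks, not to its change.
- **Rules for laboratory results.** No denominator, window or handling of absent results is stated. Blinded staff "extracted HIV primary care appointment history from the medical record with disagreements reconciled by a third reviewer", which covers appointments. For exit assessments and interviews, "we will allow a window of approximately 2 weeks prior and 4 weeks after the week-24 date"; that sentence does not mention laboratory results.
- **Primary outcome.** Retention means "having at least one visit attended in HIV clinic at both time periods (weeks 1-16 and 17-32) post-randomization".
- **Use.** The Data analysis paragraph says "we will use these data to inform power calculations for a subsequent large-scale trial".

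**The concern.** A Chi-square test compares counts of people across categories. A change in CD4 is a number on a continuous scale, so some undisclosed step must turn it into categories or the test was not the one applied. A reader cannot tell what was estimated. A Chi-square result also yields no difference in cells/microliter with an interval, although the Intervention evaluation text puts interval estimates at the centre of the analysis.

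The lesser point concerns who is counted. The intervention is meant to bring people to clinic, and the laboratory values come from care records. An arm with better attendance may therefore have more results. Suppression among people with results then compares groups formed after randomisation. Suppression documented among all randomised keeps the randomised groups but includes any effect of retention on being tested. The two answer different questions and can differ in sign. Without a stated denominator, the pilot's suppression figure cannot be interpreted or safely reused.

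**Working it through.** The plan gives no power, precision or rate for these outcomes, so there is no figure of its own to reproduce. Only the 75 to be randomised comes from the documents; every other input below is an assumption, including roughly equal allocation.

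**CD4: outcome against test**

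At least three analyses fit the text: follow-up CD4 split at a threshold, change split at a threshold, or a multi-category table of either. Each can give a different answer. Splitting at the median has a relative efficiency of 2/π = 0.637 against comparing means, if values are normal and the shift is small.

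For precision, let baseline and follow-up have equal SD and correlation ρ. Relative to comparing follow-up values alone, the variance of the arm difference is:

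- change score: 2(1-ρ)
- regression on arm and baseline: 1-ρ²
- ratio of regression to change score: (1-ρ²)/[2(1-ρ)] = (1+ρ)/2, which is below 1 whenever ρ < 1

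With SD 250 and 37.5 per arm, the follow-up-only 95% half-width is 1.96 × 250 × √(2/37.5) = 113 cells/microliter. The others follow by multiplying by the square root of the relative variance.

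| ρ | Change score | Regression | Variance ratio |
|---|---|---|---|
| 0.5 | 113 | 98 | 0.75 |
| 0.7 | 88 | 81 | 0.85 |
| 0.8 | 72 | 68 | 0.90 |

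Half-widths scale with the SD: at ρ = 0.7, regression gives 65 for SD 200 and 97 for SD 300. Regressing the change on arm and baseline gives the same arm coefficient as regressing the follow-up value, so the plan's outcome is preserved.

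**Suppression: effect of the denominator**

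Assume no true effect on suppression. In either arm 70% would attend, of whom 90% are suppressed (0.70 × 0.90 = 0.63). A share m attends only if treated, and the remaining 0.30-m never attend; in both of these groups a share s is suppressed. A share q of non-attenders still has a result.

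- Intervention: with a result, 0.70 + m + q(0.30-m); documented suppressed, 0.63 + sm + qs(0.30-m).
- Control: with a result, 0.70 + 0.30q; documented suppressed, 0.63 + 0.30qs.

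For m = 15%, s = 40%, q = 50%:

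- among people with results: 0.72/0.925 - 0.69/0.85 = 0.778 - 0.812 = -3.3 points
- documented among all randomised: 0.72 - 0.69 = +3.0 points

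Range (intervention minus control, in points):

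| m | s | q | With results | All randomised |
|---|---|---|---|---|
| 5% | 40% | 50% | -1.2 | +1.0 |
| 10% | 40% | 50% | -2.3 | +2.0 |
| 15% | 40% | 50% | -3.3 | +3.0 |
| 15% | 40% | 0% | -8.8 | +6.0 |
| 15% | 40% | 75% | -1.5 | +1.5 |
| 15% | 40% | 100% | 0 | 0 |
| 15% | 65% | 0% | -4.4 | +9.8 |
| 15% | 90% | 0% | 0 | +13.5 |

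A harsher setting has 60% always tested (85% suppressed), 10% to 30% tested only in the intervention arm (40% to 70% suppressed), and no other results. It gives -2 to -15 points and +4 to +21 points.

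**Sampling error.** The half-width is 1.96 × √[p(1-p)(1/n₁+1/n₂)]. With 38 v 37 it is 16.2 points at p = 85% and 20.7 at p = 70%. The Intervention evaluation text says "Estimated conservative rate of attrition is 30" percent. If that applied to laboratory results, which the plan does not say, then 75 × 0.70 = 52.5, and 26 v 26 gives 19.4 to 24.9 points.

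**The case against.** **It is a pilot, and the sentence may be shorthand.** The plan disclaims efficacy, and the same paragraph uses t-tests for baseline characteristics, so CD4 may have been handled suitably and described loosely. This limits the severity. It does not remove the point: CD4 is expressly listed under the Chi-square, with a 0.05 threshold.

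**The suppression illustration rests on invented rates.** That is correct. Dependence of availability on arm is an inference from the data source and the intervention's aim, not something the documents report. The figures show what could happen, not what did.

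**Stronger readings that do not hold.** A reader might infer that both suppression measures are wrong. Documented suppression among all randomised is a legitimate outcome, and the plan never says it targets suppression regardless of documentation; the supportable criticism is that the choice is unstated. A reader might also apply the window of about -2 to +4 weeks to laboratory results and conclude that retained participants could miss it. The plan sets that window for exit assessments and interviews only, so the conclusion does not follow. Finally, a reader might infer that a biased suppression difference will drive the next trial's size. The plan says only that its data will inform power calculations, its primary outcome is retention, and it doubts that an effect size is justified.

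**The analysis is reported in the past tense.** This stands: new rules would be post hoc, and disclosure of what was done comes first.

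**Conclusion.** The CD4 mismatch is established from the text alone and needs no assumed rate: a change in count is paired with a test for categories, and no categories are given. The precision gain from baseline adjustment (variance 0.75 to 0.90 of a change-score comparison for ρ of 0.5 to 0.8) depends on assumed correlations, but its direction does not.

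The suppression point is a reporting gap. Under the central assumptions the denominator moves the comparison from -3.3 to +3.0 points with no true effect, well inside sampling error. The difference among people with results is also 0 if those without results are suppressed as often as attenders. In the most extreme setting tried, the documented difference reaches +21 points, about the size of the half-width at 70% suppression (20.7). No bias in the trial's actual results has been shown. Overall severity is modest.

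**What to change.** In the Data analysis paragraph:

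1. Replace the Chi-square for CD4 with a linear regression of follow-up CD4 on arm and baseline CD4, separately at weeks 24 and 48. Report the adjusted difference with a 95% confidence interval, and state that it applies only to people with results.
2. Tabulate the number with an HIV RNA and a CD4 result by arm at weeks 24 and 48.
3. Report suppression both among all randomised, labelled as including any retention effect, and among those with a result, each with a confidence interval.
4. State the laboratory window actually used, baseline included, and how absent results were handled. Label any rule set after results were seen as post hoc.

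The cost is revised wording, light programming and a few extra tables; no new participants or visits are needed, and the baseline CD4 is already required by the outcome definition. Some re-extraction is possible, because the plan does not say how many results or dates were taken per person. The CD4 regression does not remove selection from absent results, and people tested elsewhere would count as undocumented in the all-randomised measure.
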